## Executive Summary

Physical inactivity increases the risk for multiple chronic diseases, early mortality, and accelerated cognitive decline in aging adults. Interventions to enhance physical activity among older adults are needed to improve health outcomes and reduce the burden on healthcare systems. We propose a remotely administered behavioural intervention that uses social motivation manipulation, and self-transcendence messages to effectively enhance physical activity in older adults. This randomized controlled trial consists of daily messaging delivered via smart-phone over 4 weeks in 120 healthy but 'at risk' older adults over the age of 60 years from the PResymptomatic EValuation of Experimental or Novel Treatments for AD (PREVENT-AD) cohort. Participants are randomly assigned to one of two groups: an intervention group, who are recruited with a child or grandchild (14 years or older) and receive socially motivating feedback, and an active control group, who are recruited without a family member. The primary outcome is the change in physical activity as measured by accelerometers following the intervention compared to a pre-intervention baseline. Recruitment takes place among current participants of the PREVENT-AD cohort as an optional sub-study. These participants have already undergone MRI and Alzheimer's disease biomarker assessment as part of the PREVENT-AD cohort. During the present sub-study, these participants will be assessed remotely using telephone/videoconference and computerized neuropsychological tests, computerized behavioural measures, and psychosocial surveys at baseline and after the intervention. Assessment of cognition, affect and fitness will serve as secondary outcome measures. Participants in each group will be offered the opportunity to participate in a cross-over second period of the study, to ensure that participants in the active control group have access to a potentially beneficial intervention and to serve as a longer-term follow-up of both groups. This study will assess the effectiveness of a novel behavioural intervention at enhancing physical activity in older adults and examine the neurobehavioural mechanisms underlying any such behavioural change.

## 1. Introduction

There is overwhelming evidence that increased exercise in older age improves cognitive, affective and physical well-being, and may prevent the progression of age-related illnesses [1]. Already, previous findings from the FINGER study, a large, long-term, randomized controlled trial suggests that multidomain interventions (targeting diet, exercise, cognitive training, vascular risk monitoring) could improve or maintain cognitive functioning in at-risk elderly people from the general population [2]. Nevertheless, despite the overwhelming health benefits of physical activity, many older adults are sedentary [3]. The Public Health Agency of Canada (PHAC) reports that on average adults spent 9.6 hours per day being sedentary [4]. The COVID-19 pandemic made it more difficult for older adults to stay physically active, as they were disproportionately impacted by the severity of the disease [5]. Isolation from other individuals including friends and family members further compounds the challenges to engage in physical activity [6]. Developing and understanding techniques that motivate older adults to engage in physical activity has the potential to impact a spectrum of health-related behaviours and to improve brain health and quality of life [7]. Motivational processes change across the lifespan [8]. Despite a decline in the neurobehavioral influence

of motivation on learning, older adults demonstrate relatively preserved reward sensitivity compared to younger adults [9].

Social rewards may be particularly salient for older adults and offer a promising avenue for physical activity engagement [10]. Social motivation constitutes an evolutionary adaptation encompassing a set of psychological dispositions and biological mechanisms that bias the individual to preferentially orient to the social world, to seek and take pleasure in social interactions, and to work to foster and maintain social bonds [11]. In younger adults, the presence of peers or friends has proven effective in motivating them to stay physically active [12]. In older adults, similar strategies seem to be effective; bringing a friend to group exercises, walking while talking with a friend, walking to a colleague's office rather than emailing, etc. [13]. Thus, there is reason to postulate that interventions that tap into these motivational processes would be effective in reducing time spent sedentary in older adults.

Self-transcendence convenes a change in an individual's mindset to focus on the well-being of others rather than self-interest [14]. Focusing on values and activities that transcend the self can allow people to see that their self-worth is not tied to a specific behaviour in question, and in turn become more receptive to subsequent, otherwise threatening health information. Health message interventions in older adults using self-transcendence priming were associated with increased activity in subregions of the ventromedial prefrontal cortex, implicated in self-related processing and positive valuation, which predicted later decreases in sedentary behaviour [14]. These findings suggest that having a positive self-transcendent mindset can increase behaviour change, in part by increasing neural receptivity to health messaging [14]. Moreover, health messaging is another potential way to bolster physical activity [15]. The framing of health messages matters. Therefore, in this study, we will use a social motivation manipulation combined with self-transcendence messaging to take advantage of both of these techniques to enhance physical activity in vulnerable older adults who have a family history of Alzheimer's disease, and thus, stand to benefit from a lifestyle change.

## 2. Objectives and Hypothesis

This remotely administered multidisciplinary pilot proposal focuses on examining the efficacy of factors that have shown promise in motivating sedentary older adults to become more physically active as well as to investigate changes in patterns of activation of the neural networks, as indexed by MRI and fMRI, that support these factors and changes in physical activity. Brain imaging data has already been collected as part of the PREVENT-AD longitudinal cohort. We will not acquire any new brain or biomarker data but rather capitalize the dataset on these participants that already exist.

**Aim 1: To determine the efficacy of a novel motivational intervention to enhance physical activity in at-risk older adults.** In a four-week two-arm randomized controlled trial with cognitively normal older adults at-risk for AD, we hypothesize that social motivation combined with positively-framed health messaging + home-based physical training will increase physical activity compared to positively-framed health messaging + home-based physical training. We will examine the extent to which any differential physical activity engendered in the two groups is maintained at the longer-term crossover baseline period post-intervention or active control. In addition, we will test the extent to which participants

at higher risk of AD differentially benefit from the intervention and changes in physical activity. The primary outcome will be objectively-measured physical activity, secondary outcomes will be cognitive performance and functional brain connectivity, and tertiary outcomes will be fitness, mood and quality of life.

**Aim 2. To determine the individual differences in cognitive processes that moderate behavioural change in older adults.** We hypothesize that individual differences in cognitive processes moderate behaviour change in older adults. Therefore, we will test the extent to which differences in adaptive decision-making (i.e., reward-effort computations) and dimensional measures of motivational traits (i.e., grit and growth mindset) moderate the effects of the intervention on change in physical activity. We will capture individual differences in motivation to exert effort for rewards using the Effort Expenditure for Rewards Task (EEfRT): This is an established computerized cognitive paradigm that maps onto the reward valuation/effort construct in the Research Domain Criteria (RDoC) framework. This approach will provide a novel, mechanistic understanding of how dimensional constructs of motivation influence adaptive decision-making and behavioural change.

**Aim 3: To define brain markers that predict successful real-world behavioural change in aging.** We will test the hypothesis that successful behavioural change (i.e., increased physical activity post-intervention versus baseline) is associated with enhanced activation of self-referential (i.e., ventromedial prefrontal cortex) and reward valuation (i.e., ventral striatum, ventral tegmental area) brain networks as indexed by task-based and resting-state fMRI. Acquisition of baseline brain imaging data will allow us to ask whether and what neuromarkers predict successful behavioural change as a function of the intervention.

The hypotheses that will be investigated in this study are:

- (1) Social-Motivation combined with self-transcendence messaging will increase physical activity in older adults, compared to an active control condition.
- (2) Enhanced brain network modularity at baseline will predict exercise-related executive function gains.
- (3) Individual differences in structural and functional network connectivity at baseline will predict change in physical activity.

To investigate hypotheses 2 and 3, we will be using previously acquired brain imaging data from the PREVENT-AD cohort study. The overarching goals of this work are to identify and understand novel strategies to enhance physical activity in sedentary older adults and to characterize individual brain and neuropsychological differences that predict behavioural change. Our ultimate goal is to develop personalized behavioural interventions in older adults that tailor persuasive health-related messaging based on an individual's neurobehavioral profile.

We believe that our intervention will provide valuable, novel information about the efficacy of promising factors to enhance physical activity, and in turn cognitive and brain health, in

sedentary older adults as well as the functional brain changes and individual differences that support these potential changes in physical activity.

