## 4. Methods/Assessments

### 4.1 Overview

In 120 sedentary and cognitively asymptomatic older adults (60 years and older) we will test whether a behavioural intervention combining social motivation, and self-transcendence messages decreases the amount of time participants are sedentary, as measured by accelerometry. We will use a stratified randomization scheme to ensure that half of the participants in each group will be randomized and stratified by their risk of developing Alzheimer's disease: to the social motivation + self-transcendence messaging (intervention) and the other half will be randomized to a daily activity monitoring group (active control). Participants will not be explicitly told to exercise as part of the study, but during the experiment they will receive messages that encourage walking or decreasing sedentary time. The primary measure of interest is decrease in sedentary behavior. All participants will be recruited from the PREVENT-AD cohort (STOP-AD Centre) at the Douglas Mental Health University Centre. Participants will be screened remotely by researchers affiliated with McGill University under the direction of [name].

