
**NOTE ON STUDY DESIGN AND SINGLE-BLINDING:** It is important to note that in order maintain the single-blind nature of the study, participants will not be specifically told that the daily messages are the study intervention. Therefore, the consent form will simply mention that some participants may receive motivational messages, but will not elaborate further.

Hence, in terms of the cross-over design, it will be described as a long-term follow up in the ICF in order to maintain the single-blind and not bias the participants. A debriefing session will be held at the end of period 1 to explain to the participants that the motivational messages were the intervention and they will be offered to cross-over into the opposite arm. See section 5.6 for more information regarding the cross-over.

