### RESEARCH ACTIVITIES:

After obtaining informed consent, participants will complete screening measures for anxiety, depression, and cognitive impairment. If they pass these screenings, they will be randomized into the intervention (social motivation + self-transcendence messaging or control group). After randomization, participants complete a baseline non-exercise cardiorespiratory fitness (CRF) estimation (using heart rate measurement), short virtual physical assessments involving walking and sitting-to-standing, and neuropsychological and behavioural assessment during the 'Consent Session' and at 'Time 1' (Figure 1).

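### The protocol states two different randomised contrasts, so the SAP's Aim 1 attribution to intergenerational social motivation is not secured

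*Protocol*

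**What the plan says.** Two places in the protocol state the contrast outright.

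- **Section 2, Aim 1.** Social motivation with positively framed health messaging and home-based physical training "will increase physical activity compared to positively-framed health messaging + home-based physical training".
- **Section 4.1, Overview.** Half of the participants are randomised "to the social motivation + self-transcendence messaging (intervention) and the other half will be randomized to a daily activity monitoring group (active control". The next sentence says of participants, without naming an arm, that they are not explicitly told to exercise, "but during the experiment they will receive messages that encourage walking or decreasing sedentary time".

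Elsewhere the comparator is only named. The Executive Summary describes intervention participants who are recruited with a child or grandchild "and receive socially motivating feedback, and an active control group, who are recruited without a family member". Hypothesis 1 in section 2 reads "Social-Motivation combined with self-transcendence messaging will increase physical activity in older adults, compared to an active control condition". Section 6b states the primary hypothesis in the same combined form against an active control. The SAP speaks only of a Control Group, and its Aim 1 asks how far intergenerational social motivation enhances physical activity, the primary outcome.

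**The concern.** Under the Aim 1 wording, both arms share messaging and training, so the difference can be read as the effect of social motivation. Under the section 4.1 wording, self-transcendence messaging is part of what differs. The same result is then the joint effect of two techniques, and a two-arm comparison cannot separate them. The Introduction presents self-transcendence messaging as an active means of changing behaviour, so it cannot be treated as inert background.

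At stake is what the primary result may be said to show. If messages differ by arm, SAP Aim 1 as worded would attribute a joint effect to one of its parts. A later reader also could not tell what controls received, and so could not interpret or replicate the comparison.

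**Working it through.** **1. The two stated contrasts.** Let S be social motivation, H health messaging, X home-based training, T self-transcendence messaging and M activity monitoring.

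- Section 2, Aim 1: (S + H + X) versus (H + X). H and X cancel, leaving S.
- Section 4.1: (S + T) versus M. This leaves S and T jointly: one estimated difference and two unknown contributions.

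**2. Text placing the messages in the intervention.**

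- The single-blinding note in section 4.2 says that "participants will not be specifically told that the daily messages are the study intervention", and that the consent form mentions only that "some participants may receive motivational messages". The debriefing then tells participants that the motivational messages were the intervention.
- Research Activities: "they will be randomized into the intervention (social motivation + self-transcendence messaging or control group".
- Section 10 refers to one arm by the names of both social motivation and self-transcendence health messaging.

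**3. Text that sets no arm limit on messages.**

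- Section 4.1: the walking-message sentence quoted above.
- Section 5.1: participants in general receive daily messages during the four weeks.
- Section 5.3: message links go to every participant at enrolment.
- Figure 2 legend: the 28-day message process runs for all other participants too.
- Section 9: the daily health messages are relied on to carry staff contact details.

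The single-blinding note could also refer only to the partner-composed messages, which the Study partner section (the second 5.6) itself calls self-transcendence messages.

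**4. Other components whose allocation is unclear.**

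- *Home-based training* is named in section 2 and section 6b but not described as a delivered component in the visible text. It sits badly with section 4.1 (no explicit instruction to exercise) and section 9 (walking and less sedentary time, not exercise training).
- *Activity feedback* is stated for the intervention arm in section 5.3. Section 5.5 syncs devices to the same vendor's app with no arm limit, and the Executive Summary's wording allows feedback to be read as part of the social manipulation.
- *The charity donation* (sections 3.8.3.c and 3.8.3.d) is limited in period 2 to those crossing into the intervention, on the same principle as period 1. That suggests an intervention-only element, but period 1 does not say so.

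**5. Does the sample size identify the contrast?** The SAP gives a difference of 10.0%, SD 14.0%, 80% power, two-sided alpha 0.05 and 30 per arm. By the normal approximation, n per arm = 2 × [14 × (1.960 + 0.8416) / 10]² = 30.77, rounded up to 31. Power at 30 per arm is 79.0%. The stated figure is therefore reproduced to within one participant per arm. The SAP does not say which contrast the 10% belongs to, so the calculation does not help choose between the two definitions.

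**The case against.** The best defence is that daily activity monitoring in section 4.1 is an arm label, not a list of contents. Controls might receive monitoring plus walking or health messages, which would fit the next sentence of section 4.1 and every item in step 3. Section 4.2 also calls the whole intervention arm a social motivation group. The SAP's phrase may likewise be shorthand for the package, which the SAP elsewhere calls an intergenerational behaviour intervention. The timeline document, the figures and the annexes were not available and may settle arm content. A combined-intervention comparison is also a legitimate pilot design.

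Much of this stands. The reading with messages in both arms is not excluded, so the two definitions are not irreconcilable on walking or health messages. Missing detail on training is weak evidence, because an annex may hold it.

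Three things do not fall away. No section states that reading. Even if it is right, it leaves open whether the self-transcendence messages are shared, because the protocol sometimes merges them with health messages and sometimes treats them as a separate technique. And the Aim 1 and section 4.1 wordings are both current text and still state different contrasts, whatever an annex says. If the SAP's phrase is shorthand, it is a shorthand that names one component for the whole.

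**Conclusion.** The point holds as a matter of definition and attribution. The protocol gives two different randomised contrasts, its other sections do not decide between them, and the SAP's wording is supported only if the social-motivation manipulation is the sole difference. The protocol's own hypothesis 1 and primary hypothesis are safer because they claim only the combined effect. Confidence is moderate, because unseen material may define the arms.

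The size is interpretive. Randomisation, outcomes and the planned model are unaffected, and no stated number is shown to be wrong.

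A reader might infer three stronger things that the documents do not support:

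- **That controls received no messages.** Several sections set no arm limit, so this cannot be concluded.
- **That the arms differ by a definite number of components.** The status of feedback, the donation and the overlap between health and self-transcendence messages is too unclear to count.
- **That the trial is underpowered for social motivation alone.** The documents give no effect for any single component, so any such figure would rest on an invented split of the 10%.

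**What to change.** 1. Reword SAP Aim 1 and the primary conclusion as the effect of the combined intervention versus the stated control, in line with hypothesis 1 and the primary hypothesis in section 6b. Keep the present attribution only if the reconciled definition shows that the arms differ solely in the social-motivation manipulation, and say whether feedback belongs to it.
2. Put one arm-by-component definition in the protocol and refer to it in the SAP. It should cover the study partner, self-transcendence messages, health or walking messages, partner-composed messages, activity feedback, home-based training (describe it or delete it) and the period 1 donation. If the timeline document or an annex already gives this, cite it in both documents.
3. Bring these places into line with it: the Executive Summary; section 2, Aim 1; sections 3.8.3.c and 3.8.3.d; sections 4.1 and 4.2 with the blinding note; Research Activities; sections 5.1 and 5.3 with the Figure 2 legend; the device paragraphs in 5.5; the Study partner section; and sections 6b, 9 and 10.

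The cost is one table or citation and some wording, with no added arm, participants or data. The downside is a less specific causal claim in the SAP if messages do differ by arm.

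### Protocol Aim 1 lists functional brain connectivity as a secondary outcome, but the plan describes no scan after the intervention from which an effect on it could be estimated

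*Protocol*

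**What the plan says.** Protocol section 2, Aim 1, sets out the two-arm randomised comparison and lists its outcomes: "secondary outcomes will be cognitive performance and functional brain connectivity". The opening paragraph of the same section says "We will not acquire any new brain or biomarker data", yet it also states a purpose "to investigate changes in patterns of activation of the neural networks, as indexed by MRI and fMRI".

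The Executive Summary says "These participants have already undergone MRI" and gives a different list: "Assessment of cognition, affect and fitness will serve as secondary outcome measures". For hypotheses 2 and 3, section 2 says "we will be using previously acquired brain imaging data from the PREVENT-AD cohort study". Section 5.5 likewise describes all imaging as already collected within the parent cohort.

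The closing text of section 2 nevertheless expects the trial to inform on brain changes that accompany a change in activity. Section 6b says the fMRI connectivity analyses will address the intervention effect as well as prediction.

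SAP Aim 1 names cognition, loneliness, self-efficacy, mood and sleep as secondary outcomes, without connectivity. SAP Aim 3 uses connectivity to predict response, but its description of the data can be read as including MRI obtained while the intervention was running.

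**The concern.** An outcome of a randomised efficacy aim has to be measured after the treatment has had a chance to act. Functional connectivity has that status in Aim 1, but the protocol describes scans that exist before the sub-study begins. If so, the outcome cannot respond to the intervention.

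What is at stake is a secondary claim. As worded, the plan leaves room for a chance baseline imbalance, or a correlation with baseline connectivity, to be reported as an effect of the intervention on the brain. A reader of both documents also cannot tell whether connectivity is an efficacy outcome or only a predictor.

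**Working it through.** **The plan's own figure.** There is none for connectivity. The only calculation is the SAP sample size, from a difference of 10.0%, SD 14.0%, 80% power and two-sided 0.05: n per arm = 2 × (1.96 + 0.842)² × (14/10)² = 2 × 7.85 × 1.96 = 30.8. That is 31 per arm against the stated 30, so it reproduces closely. Its SD comes from a physical activity intervention, and it does not bear on this point. The check is therefore one of timing.

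**Is there a post-intervention scan?**
- Protocol section 2: no new brain data; existing cohort scans serve hypotheses 2 and 3.
- Protocol Executive Summary and section 5.5: imaging already done.
- Protocol section 5.1: every session is remote, and the post-intervention session repeats surveys and neuropsychological tests.
- Protocol section 6b, outcome table: steps, sedentary time, moderate-to-vigorous activity, cadence and walking bouts. There is no imaging row.
- Protocol section 6a: lists MRI among the stored data, without a date or visit.
- SAP Aim 3: ambiguous on timing, as described above, and gives no scan visit or time point.

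Post-intervention scans scheduled in the available text: none.

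**What follows if the scans predate randomisation.** Let C be a participant's connectivity on such a scan. C is the same whichever arm is later assigned, so the effect of assignment on C is C − C = 0 for every participant. A change score would need a second, later value, which is not scheduled. Among all randomised participants with scans, the expected arm difference is zero. Among completers it can differ from zero if dropout depends on both arm and connectivity, but that would be selection and not an effect on the brain.

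**Scale of chance imbalance (illustrative).** Assume equal arms, a usable scan for everyone and a marker SD of 1. The SD of the arm difference is √(1/(N/2) + 1/(N/2)) = √(4/N).
- N = 60 (SAP): √(4/60) = 0.258; × 1.96 = 0.506.
- N = 120 (protocol): √(4/120) = 0.183; × 1.96 = 0.358.

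In 40,000 simulated trials at each size, a two-sided 0.05 t-test rejected in 4.8% (30 per arm) and 5.0% (60 per arm), which is simply the significance level. A larger sample tightens the spread around zero and reveals nothing about the intervention.

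**What remains estimable.** Baseline connectivity can be related to later change in activity or cognition. That is how hypothesis 3 and SAP Aim 3 use it for activity, and how hypothesis 2 uses baseline modularity for executive function gains.

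**The case against.** The strongest reply is that this is one stray phrase. The outcome table omits imaging, hypotheses 2 and 3 use it only at baseline, and the SAP uses connectivity only as a predictor. No passage specifies a between-arm test of connectivity. All of this stands, so the imbalance figures above show scale and do not describe a planned analysis. A reader might infer that the trial is set up to produce a false positive brain effect; the documents do not support that. Nor is the SAP's omission of connectivity from Aim 1 a second error, because it fits the predictor role. The phrase still needs correcting: Aim 1 calls connectivity an outcome, and section 6b lists the intervention effect separately from prediction.

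A second reply is that later scans may exist. Section 5.5 describes the parent cohort as ongoing, SAP Aim 3 is open to that reading, and the figures, timeline document and assessment spreadsheet were not visible here. This limits certainty about timing. It does not supply a scan, a window or an analysis, and a new trial scan shown elsewhere would contradict section 2.

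A third is that some brain wording is harmless. Aim 3 says successful change "is associated with enhanced activation of self-referential" and reward networks, and section 6b speaks of enhanced connectivity. A reader might take both as untestable claims of change. Hypothesis 2 uses the same adjective for a baseline level, so both can be read that way and need clarification only. The same goes for the Aim 3 sentence "Acquisition of baseline brain imaging data will allow us to ask whether and what neuromarkers predict successful behavioural change as a function of the intervention", which fits awkwardly with reliance on existing scans.

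**Conclusion.** The contradiction is in the text: section 2 makes functional connectivity a secondary efficacy outcome and rules out new brain data. As the design is described, an intervention effect on connectivity cannot be estimated at 60, at 120 or at any other number. The stated aim of studying activation changes, the brain-change language closing section 2 and the fMRI intervention-effect wording in section 6b share the problem.

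The conclusion about estimability rests on the scans predating randomisation. The Executive Summary and sections 2 and 5.5 indicate this, but neither document gives scan dates relative to randomisation. The absence of a scheduled scan was checked from text only.

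The point does not reach the primary comparison or hypotheses 2 and 3. A reader might infer that the imaging work as a whole is invalid; that does not follow, because baseline scans can serve as predictors.

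**What to change.** 1. In Protocol section 2, remove functional brain connectivity from the Aim 1 secondary outcomes and treat it as a baseline predictor of change in physical activity, consistent with the baseline-predictor role of imaging in hypotheses 2 and 3 and SAP Aim 3. The Executive Summary and SAP lists also omit it, but they differ from each other in other items, so this change alone will not align them.
2. Delete or reword the brain-change wording at the start and end of section 2 and the fMRI intervention-effect wording in section 6b. State that enhanced activation (Aim 3) and enhanced connectivity (section 6b) mean a higher baseline level.
3. Reconcile SAP Aim 3 with Protocol sections 2 and 5.5 by stating which scans are used and when each was taken relative to that participant's randomisation.

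If timed post-intervention scans in both arms do exist, both documents should say so, and connectivity can remain an outcome with a stated time point.

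The cost is wording in two documents and no new data. The trial gives up a claim of change in the brain. A group-by-marker term, to match the Aim 3 phrase about prediction as a function of the intervention, is optional and exploratory, and is not part of this fix.
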